Expiratory muscle function in critically ill ventilated patients

NTC:

Date of approved by METC: February 14, 2017

Date of amendment approved by METC: May 22, 2019

Rationale	
Inspiratory muscle weakness develops rapidly in ventilated critically ill patients¹⁻⁴ and is associated with adverse outcome, including prolonged duration of mechanical ventilation and mortality.⁵⁻⁷ Surprisingly, the effects of critical illness on expiratory muscle function have not been studied.
 
The main expiratory muscles are the abdominal wall muscles, including the external oblique (EO), internal oblique (IO) and transversus abdominis muscles (TRA).^{8,9} These muscles are activated when respiratory drive or load increases, which can be during e.g. exercise,¹⁰⁻¹² diaphragm fatigue,¹³ increased airway resistance, or positive airway pressure ventilation.¹⁴ The abdominal wall muscles are also critical for protective reflexes, such as coughing.¹⁵ Reduced abdominal muscles strength may lead to decreased cough function^{16,17} and thus inadequate airway clearance.¹⁸ This will lead to secretion pooling in the lower airways, atelectasis, and ventilator associated pneumonia (VAP).^{19,20} Studies have shown that decreased cough function is a risk for weaning failure and (re)hospitalization for respiratory complications.²¹ Further, high mortality was found in patients with low peak expiratory flow.²²
 
Considering the importance of a proper expiratory muscle function in critically ill patients, it is surprising that the prevalence, causes, and functional impact of changes in expiratory abdominal muscles thickness during mechanical ventilation (MV) for critically ill patients are still unknown.

------------------	--

Ultrasound is increasingly used in the ICU for the visualization of respiratory muscles. In a recent pilot study we confirmed the feasibility and reliability of using of ultrasound to evaluate both diaphragm and expiratory abdominal muscle thickness in ventilated critically ill patients (manuscript in preparation). An example of such measurement can be found in figure 1. Accordingly, the primary aim of the present study is to evaluate the evolution of abdominal expiratory muscle thickness during MV in adult critically ill patients, using ultrasound data.

Figure 1. Left: ultrasound of the abdominal expiratory muscles (EO, IO, TRA). Right: anatomical overview of the abdominal muscles. RA = rectus abdominis, less involved in respiration

Objective

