Primary objective: to establish the effects of critical illness and mechanical ventilation on thickness of the abdominal expiratory muscles.

Secondary objectives:

- to establish the effect of changes in abdominal expiratory muscle thickness on the expiratory muscle function.

	
 - to establish the correlation between changes in thickness of the abdominal expiratory and inspiratory muscles. - to study whether changes in the thickness of the abdominal expiratory muscles also affects weaning outcome, and ICU readmission due to respiratory complications.
Study design	Prospective cohort study.
Study population	Patients who have been mechanically ventilated at the intensive care unit (ICU)
Inclusive criteria	
 - Age > 18 years - Invasive mechanical ventilation < 48 hours - Expected duration of mechanical ventilation > 72 hours
Exclusive criteria	
 - Past medical history of neuromuscular disorders - Mechanical ventilation > 48 hours within the current hospital admission - BMI > 35 kg/m² - Pregnant women - Open abdominal wounds at proposed location of the ultrasound probe, due to recent abdominal surgery
Sample size	100 subjects
Recruiting subjects	
Because mechanical ventilation is a requirement for eligibility, the participants frequently will be incapable of consent at the time of inclusion. Therefore, we will ask delayed informed consent from the patient as soon as he/she is capable of providing consent.
 
If patients are not able to give consent during their hospital stay, we will send an opt-out letter to the patient.

Intervention	Data from ultrasound measurements and from the electronic patient record will be obtained / analyzed. One additional blood sample will be obtained within 24 hours after inclusion, during planned blood collection (from arterial line or venous puncture).
Study endpoint	- Thickness of the abdominal expiratory muscles (external oblique, internal oblique, transverse abdominis muscle), during the inspiratory and expiratory phases of breathing.

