Statistical Analysis Plan	
SPSS statistical software package version 22.0 or R software for statistical computing version 3.2.0 will be used.
 
Primary endpoint: change of thickness of expiratory abdominal muscles during MV. Change in thickness will be presented as ratio change compared to baseline, to account for inter-subject variation in baseline thickness. The Wilcoxon signed-rank test will be used to compare changes in baseline and nadir values.
 
Association of categorical independent variables (such as sex, use of corticosteroids during ICU stay, sepsis on admission, etc.) with nadir change in expiratory muscle thickness will be assessed using a Mann-Whitney U test. Association of continuous independent variables (such as duration of mechanical ventilation, days taken to wean, inflammation at inclusion, etc.) with nadir change in expiratory muscle thickness will be assessed using a linear regression model, with change in expiratory muscle thickness as dependent variable. Correlation between change in thickness during the acute stage of MV (5 days) with the total time spent on the ventilator will be examined using a linear regression model.
 
Correlation between diaphragm and expiratory muscles
 
Correlation between change in expiratory muscle thickness and change in diaphragm thickness will be assessed with Pearson's correlation test to compare population means. The difference between change in

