	
expiratory muscle thickness and change in diaphragm thickness will be assessed with a Student's t-test that is paired per subject. This will be done by using the change in thickness between baseline and the last data point obtained. Second, this will be evaluated by using the slope of the thickness curves assessed with a goodness of fit model. We will use a goodness of fit model to first describe the course of both diaphragm and expiratory muscle thickness for each subject. The type of model will be determined after data is obtained.
 
Subgroup analysis
 
Based on the outcomes of these analyses, a subgroup analysis may be performed to compare the subjects with high change in expiratory muscle thickness, to a group with low change in expiratory muscle thickness. A cutoff value to divide these groups will be determined based on how data will emerge. Variables as respiratory function measurements can be compared between groups with a Student's t-test, using group average values. Further, a Kaplan-Meier survival analysis will be carried out to quantify differences in time to wean between groups.

Referenties
	

- and endotracheal tube pressure with bilateral anterolateral magnetic phrenic nerve stimulation in patients in the intensive care unit. *Crit Care Med* 2001; 29:1325-31.

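### Nadir change has no common time window, so regressing it on ventilation duration or days to wean can produce a link with longer stay if scans continue through ventilation

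*Combined protocol and SAP*

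**What the plan says.** The primary endpoint in the Statistical Analysis Plan is "change of thickness of expiratory abdominal muscles during MV", with the scale given as "Change in thickness will be presented as ratio change compared to baseline". Baseline is compared with the nadir. The plan then takes nadir change as the dependent variable in linear regressions on continuous variables "such as duration of mechanical ventilation, days taken to wean, inflammation at inclusion, etc.) with nadir change in expiratory muscle thickness". It gives no day or window for the nadir, no scan schedule, no last scan day, and no term for number of scans or time observed.

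Other parts of the document bear on this:

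- The Rationale aims to "evaluate the evolution of abdominal expiratory muscle thickness during MV in adult critically ill patients".
- The inclusion criteria admit patients ventilated for under 48 hours, with "Expected duration of mechanical ventilation > 72 hours" and no upper limit.
- A secondary objective is "to study whether changes in the thickness of the abdominal expiratory muscles also affects weaning outcome".
- The plan has a separate regression of "change in thickness during the acute stage of MV (5 days) with the total time spent on the ventilator", which does name a window.
- The diaphragm comparison works by "using the change in thickness between baseline and the last data point obtained".
- The Subgroup analysis may split patients into high and low thickness change at a data-driven cutoff and compare time to wean by Kaplan-Meier.

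**The concern.** Duration of ventilation is used to explain an outcome that it may partly determine. If patients are scanned for as long as they are ventilated, a longer stay gives more chances to record a low value, whatever the muscle is doing. Days to wean inherits the problem through its correlation with duration.

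The study could then report that thinning accompanies long ventilation or slow weaning when the result only reflects longer observation. Where muscles truly thin, part of the association is real cumulative loss. Even so, a nadir that may fall on any day cannot show that faster thinning goes with longer ventilation, nor that thinning affects weaning. For that objective the timing also matters: a nadir reached late in the stay cannot be read as preceding a weaning course already under way.

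**Working it through.** **No plan figure to reproduce.** The sample size of 100 comes without alpha, power, effect size or SD, and the point does not depend on it. The plan states no alpha for these tests; two-sided 5% is assumed.

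**Step 1: unequal observation time.** Entry is possible up to 48 h into ventilation. If the expected 72 h means total ventilation, expected follow-up starts at 72 − 48 = 24 h. If it means remaining ventilation, it starts at 72 h. On either reading there is no upper limit.

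**Step 2: direction.** For patient i with scans m₀, m₁, …, m_k, nadir change is y = min(m₀, …, m_k)/m₀ − 1. Adding scan k+1 can leave the minimum unchanged or lower it, never raise it. The direction therefore needs no clinical assumption, only that the number of scans rises with duration.

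**Step 3: size from noise alone.** With constant true thickness and log-normal scan error of CV 5% (assumed), mean y is −4.0% with 2 follow-up scans, −6.0% with 5 and −8.2% with 14. Going from 2 to 14 scans therefore adds 8.2 − 4.0 = 4.2 percentage points of apparent thinning.

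**Step 4: false significance.** Simulated studies had n = 100 and duration D counted from the baseline scan. D was lognormal with median 7 d and log-SD 0.69, restricted to at least 3 d or at least 0.5 d. Scans were every 1 or 2 days and CV was 5%. In every row, true thickness change is unrelated to D. All of these values except n are assumptions.

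| Scenario | Regression on duration significant at 5% |
|---|---|
| No true change, scans to end of ventilation | roughly 63-90%, always negative |
| Patients differ (mean zero, SD 10-15%), early change then plateau | roughly 20-55% |
| No true change, daily scans stop at day 7 | 12-26% |
| No true change, scans stop at day 5, all patients kept | about 6-16% |
| Nadir within 5 days, only patients ventilated at least 5 days | about 5% |

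In the first row, the low end is the 3-day minimum with daily scans and the high end is the 0.5-day minimum with two-day scans. Changing CV hardly matters: separate runs at 3%, 5% and 10%, with a median of 8 d, gave 66-70% with daily scans and 76-81% with two-day scans. The mean correlation there was −0.23 to −0.28, or 0.23² = 5% to 0.28² = 8% of variance. That is weak, but n = 100 has 80% power for a correlation of about 0.28.

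**Step 5: days to wean.** With no true change and scans throughout, the false-significance rate depends on the correlation of days to wean with log duration:

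| Correlation | Rate |
|---|---|
| 0 | 4-5% |
| 0.3 | 11-13% |
| 0.5 | 21-28% |
| 0.7 | 37-47% |
| 0.9 | 57-70% |

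**Step 6: who leaves a day-5 landmark.** P(D < 5) = Φ(ln(5/7)/0.69) = Φ(−0.488) = 0.313, and P(D < 3) = Φ(ln(3/7)/0.69) = Φ(−1.228) = 0.110. With the 3-day minimum the loss is (0.313 − 0.110)/(1 − 0.110) = 23%. With the 0.5-day minimum it is 31%.

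**The case against.** **The schedule is not stated.** This is the strongest objection. The wording about evolution during ventilation and a last data point would also fit a short fixed schedule with dropouts, and the only window the plan names is 5 days. If scans stop at day 5, little of the artefact remains. This stands, and the point is conditional on it. A reader might infer that the study will report a false link in 63-90% of cases; the documents do not support that. Against a short schedule, an open-ended endpoint and nadir suggest longer scanning, and a separately labelled 5-day analysis would add little if all scans ended then.

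**Constant thickness in every patient is an extreme null.** This also stands, and the plateau row of the table is the answer to it. Its range depends on the settings: with two-day scans and the 0.5-day minimum, one set of runs gave 29-71%.

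**The 5-day regression already covers this.** It does so for total ventilator time only, and nothing gives it precedence over the nadir regression.

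**Weaning is also analysed as an outcome.** A reader might infer that the plan studies weaning only in the reverse direction. It does not: the optional Kaplan-Meier comparison treats time to wean as the outcome. Its high and low change groups have no common window either, so longer-ventilated patients have more opportunity to enter the high-change group.

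**Duration is a legitimate exposure.** The primary objective concerns the effect of critical illness and ventilation on thickness. A reader might infer that duration should simply be dropped; the objective does not support that. The fault lies in pairing duration with an open-window nadir.

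**Inflammation at inclusion** sits in the same list, but it is fixed at baseline. With no relation to duration its rate stays at 5%; it is affected only as far as it correlates with duration.

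**Conclusion.** The point holds in conditional form. As written, the regressions of nadir change on duration of ventilation and on days to wean share no common window and have no adjustment for observation time. If scanning follows patients through ventilation, the duration regression is biased towards a deeper nadir with longer stay, and days to wean is biased in proportion to its link with duration. The direction follows from the definition of a minimum. The size rests on assumed durations, scan intervals, CV and change patterns, none of which the documents give. It runs from a serious false-positive rate (roughly 63-90% with no true change, roughly 20-55% with early change that plateaus) down to about 6-16% if scans end at day 5. An observed association need not be wholly artefact, but the planned analysis cannot separate longer observation or cumulative exposure from faster thinning. This concerns the association analyses; it is not a finding about the primary Wilcoxon comparison.

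**What to change.** 1. State the scan schedule and last scan day, with a scan near day 5 counted from the baseline scan, since entry can be up to 48 h into ventilation.
2. Do not interpret the open-window nadir regressions on duration of ventilation or days to wean.
3. For the weaning objective, analyse days to wean (including the Kaplan-Meier groups) and total ventilator time as outcomes of the 5-day ratio change. Restrict this to patients still ventilated at day 5 and count time from that day.
4. If ventilation time is of interest as an exposure, model the repeated thickness measurements against time on the ventilator with a mixed model that allows curvature. A per-patient straight-line slope is not a safe substitute: with a 10% mean loss that plateaus, it was itself falsely related to duration in 56-100% of simulations, in the opposite direction.

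The cost is SAP wording and a stated schedule. About 23-31% of patients (assumed median 7 d) leave the landmark analysis, whose conclusions then apply only to those ventilated at least 5 days. They still contribute to the mixed model, which must in turn assume that the end of ventilation is uninformative given the thickness already observed. Landmark power is modest: about 34% if early change truly correlates −0.3 with log duration, and 64% at −0.4, under the same kind of assumptions. The nadir regression would detect more, but it cannot tell a true effect from longer observation.

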Study parameters	
 - Thickness of the diaphragm muscle - Inflammatory markers (TNF-alpha, IL-6, IL-10) at inclusion (measured from blood sample using ELISA technique). - Respiratory function parameters: maximum inspiratory pressure (MIP), maximum expiratory pressure (MEP), cough peak flow (CPF), diaphragm pressure and diaphragm electrical activity (in selected patients with these measurements available in clinical practice). - Mechanical ventilation parameters. - Weaning outcome - Ventilator associated pneumonia (VAP) - Follow-up of 6 weeks: readmission to ICU / hospital, reason for readmission, pneumonia acquired after discharge when subject is hospitalized. - Critical illness parameters (e.g. medication, APACHE II score) - Patient characteristics (e.g. gender, age, neurological and cardiopulmonary co-morbidities, BMI) 
This data will be retrieved from the electronic patient record and anonymously filed in a database.
 
Data on muscle thickness (thickness of diaphragm muscle and expiratory muscles) will be collected directly

	from ultrasound measurements on the ultrasound device.

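### The regression on total ventilator time has no rule for death on the ventilator, so its slope mixes weaning with death and cannot by itself answer the weaning objective

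*Combined protocol and SAP*

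**What the plan says.** The combined protocol and SAP sets as a secondary objective "to study whether changes in the thickness of the abdominal expiratory muscles also affects weaning outcome, and ICU readmission due to respiratory complications".

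Two firmly planned analyses in the Statistical Analysis Plan use ventilator or weaning time:
- The 5-day thickness change is related to ventilator time: this "with the total time spent on the ventilator will be examined using a linear regression model". The plan does not say which of the two is the dependent variable.
- A linear regression of nadir change uses continuous independent variables "such as duration of mechanical ventilation, days taken to wean, inflammation at inclusion, etc".

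The only time-to-event method is in the subgroup analysis, which is optional and has a cutoff chosen from the data: "a Kaplan-Meier survival analysis will be carried out to quantify differences in time to wean between groups". It has no rule for death either.

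Study parameters lists weaning outcome without a definition. Its follow-up entry reads "Follow-up of 6 weeks: readmission to ICU / hospital, reason for readmission, pneumonia acquired after discharge when subject is hospitalized". Neither entry mentions death. Mortality appears only in the Rationale.

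**The concern.** Recorded ventilator time ends when the patient is liberated or dies. Linear regression carries no event type, so a patient liberated on day 9 and a patient who dies on day 9 are the same data point. The slope answers how thinning relates to the total time on the machine. The objective asks how it relates to weaning.

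Death is foreseeable in critically ill patients enrolled with "Expected duration of mechanical ventilation > 72 hours". At stake is the reading of the weaning result. Longer ventilation in thinners could mean slower weaning or fewer deaths. Shorter ventilation could mean faster weaning or more deaths. The second regression has a further gap: days taken to wean has no value for a patient who dies ventilated.

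**Working it through.** **Inputs.** From the documents: 100 subjects, a 5-day change, and linear regression. The documents give no death rate, effect size, SD or significance level, so there is no plan figure to reproduce. Assumed: two-sided 5% test; thinning x standard normal; constant hazards from a day-5 landmark; total exit rate 0.10 per day at mean thinning; death share s = 10, 20, 30 or 40%; no other censoring; all 100 patients in the analysis. W and D are the hazard ratios per SD of thinning for weaning and for death. Each setting has 4,000 simulated trials.

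**Step 1: what the slope estimates.** The exit rate is h(x) = 0.10 × [(1−s)·W^x + s·D^x], and the mean time after day 5 is 1/h(x). At mean thinning the slope is −10 × [(1−s)·ln W + s·ln D] days per SD, which mixes both effects. With simple regression the p-value is the same whichever variable is dependent.

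**Step 2: no weaning effect (W = 1).** Trials with a significant false result in the stated direction (chance level 2.5% in one direction):

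| D | False finding | 10% deaths | 20% | 30% | 40% |
|---|---|---|---|---|---|
| 0.5 | longer | 10% | 27% | 48% | 69% |
| 0.75 | longer | 5% | 8% | 13% | 19% |
| 1.25 | shorter | 3% | 6% | 9% | 14% |
| 2 | shorter | 10% | 27% | 49% | 69% |

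At D = 1 rejection stays near 5% in total. A cause-specific Cox model for weaning rejects in 5-6% throughout.

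**Step 3: true slowing of weaning (W = 0.75).** Two no-death comparators are possible.
- Same total exit rate, all exits liberations: 10 × 0.288 × exp(0.288²/2) = +3.0 days per SD, detected in 78%.
- Same weaning hazard, death removed: divide by (1−s), giving +3.3/+3.8/+4.3/+5.0 at 10/20/30/40% deaths.

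Slope in days per SD (share of trials that detect it):

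| Deaths | D = 1 | D = 1.25 | D = 1.5 | D = 2 |
|---|---|---|---|---|
| 10% | +2.6 (68%) | +2.3 (59%) | +2.0 (48%) | +1.4 (26%) |
| 20% | +2.3 (59%) | +1.8 (39%) | +1.2 (22%) | +0.5 (5%) |
| 30% | +2.0 (47%) | +1.2 (20%) | +0.6 (6%) | −0.2 (1%) |
| 40% | +1.7 (37%) | +0.8 (10%) | 0.0 (2%) | −0.9 (0%) |

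Check at 30%, D = 1: −10 × 0.7 × ln 0.75 = +2.0. Every cell lies below both comparators.

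**Step 4: when the sign reverses.** Setting the Step 1 slope to zero gives D = W^(−(1−s)/s) = 13.3/3.2/2.0/1.5 at 10/20/30/40% deaths. That is the local slope at mean thinning. The straight line fitted over all x has slope E[x/h(x)]. Integrated numerically, this crosses zero somewhat earlier, at D = 4.2/2.4/1.8/1.5. On either calculation, reversal needs a strong death effect unless deaths are common.

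**Step 5: excluding deaths.** With constant hazards, the time of exit at a given x has mean 1/h(x) whether the exit is death or liberation. Dropping deaths therefore changes only which x values remain. At 30% deaths, W = 0.75 and D = 1/1.25/1.5/2, the slope is +1.9/+1.3/+0.8/+0.2 after exclusion, against +2.0/+1.2/+0.6/−0.2 with everyone.

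**Step 6: shape of the hazard.** With Weibull shapes 0.7 and 1.5 (30% deaths, D = 1) the slope is 65% and 69% of the same-exit-rate comparator, against 65% with constant hazards.

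**The case against.** The strongest reply is that the regression need not be a weaning analysis. The plan calls it a correlation and places it with the primary endpoint, and time on the ventilator is a valid measure of exposure for patients who die. That stands: as a description of ventilator use it is well defined. But then no firmly planned analysis of ventilator or weaning time isolates weaning. Weaning outcome is undefined, so it may or may not capture death on the ventilator; the documents do not show that it does.

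A second reply is that the sizes have no documentary basis. That also stands. The large false-positive rates need D of 0.5 or 2 with 30-40% deaths.

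Third, the Cox model's good showing (hazard ratio 0.74-0.75 at W = 0.75) is partly built in. The data were generated under proportional hazards with thinning the only covariate. In this cohort, illness severity may drive thinning, weaning and death together, and an unadjusted Cox model would not remove that confounding.

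A reader might infer that the regression exaggerates a real weaning effect when deaths concentrate in patients who do not thin. This is not supported. At D = 0.75 the slope is +3.0, equal to the same-exit-rate comparator. At D = 0.9 and 30% deaths it is +2.4, which is attenuation. At D = 0.5 it is about +3.4/+3.8/+4.2/+4.7, above +3.0 but level with or below the same-weaning-hazard values of +3.3/+3.8/+4.3/+5.0. Whether there is inflation depends on the comparator, so none is claimed.

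**Conclusion.** The omission is real and matters for interpretation. Followed as written, the plan cannot separate slower weaning from a difference in death. With no weaning effect, the false association can go either way, and its sign follows the link between thinning and death. With a true slowing of weaning, the slope is attenuated when death is unrelated to thinning or more common in thinners: at 30% deaths and D = 1 it is +2.0 days per SD, against +3.0 or +4.3 depending on the comparator.

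A reader might also infer from the Rationale that thinners die more often, so that the direction is known. The Rationale says "high mortality was found in patients with low peak expiratory flow", but by its title the study cited there concerns cough flow and extubation outcomes, not deaths before liberation. Nothing links thickness change to death on the ventilator. The Rationale itself states that the prevalence, causes and "functional impact of changes in expiratory abdominal muscles thickness during mechanical ventilation (MV) for critically ill patients are still unknown". All sizes are therefore illustrative.

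The point concerns secondary analyses only. The baseline-to-nadir Wilcoxon test does not use this regression. The change should be made, but the study does not stand or fall on it.

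**What to change.** - Add to Study parameters: death on the ventilator with its date, and the date of successful liberation with a definition.
- Define a day-5 landmark set: alive, ventilated and with a day-5 scan. Count and describe patients who left earlier, since eligibility rests only on an expected duration above 72 hours.
- As the weaning analysis, replace the linear regression by a cause-specific Cox model for liberation on the 5-day change. Report with it the matching model, or at least the counts, for death on the ventilator. Censor patients still ventilated at the end of data collection.
- State how days taken to wean is treated for patients who die.
- If the optional Kaplan-Meier analysis is used to report weaning probabilities, use the cumulative incidence with death as a competing event.
- The linear regression may stay as a description of ventilator use only. Ventilator-free days may be added if labelled a composite of weaning and death.

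The cost is a few record fields and some SAP wording; that the electronic patient record holds these dates is an assumption. There will be two estimates in place of one slope. The death estimate is imprecise if deaths are few: at 10% deaths, D = 2 is detected in 62%. The weaning model can also detect less than the regression (58% against 95% at W = 0.75, D = 0.5 and 30% deaths), because the regression counts a death effect as a weaning effect.

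### The only named analysis of respiratory function, and the only time-to-event analysis of weaning, split continuous thickness change in two; for a roughly normal change with a linear effect, the t-test on function loses about 36% to 46% of the information

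*Combined protocol and SAP*

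**What the plan says.** The combined protocol and SAP lists two secondary objectives that depend on thickness change as an exposure: "to establish the effect of changes in abdominal expiratory muscle thickness on the expiratory muscle function", and "to study whether changes in the thickness of the abdominal expiratory muscles also affects weaning outcome, and ICU readmission due to respiratory complications".

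The Statistical Analysis Plan keeps that exposure on a continuous scale: "Change in thickness will be presented as ratio change compared to baseline". It then plans linear regressions that leave it continuous. One has nadir change as the dependent variable and an open-ended list of continuous explanatory variables, which includes ventilation duration and days to wean. Another relates the change over the first 5 days to total ventilator time. MIP, MEP and cough peak flow are not named in either.

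Respiratory function appears only under Subgroup analysis. That analysis is conditional: "Based on the outcomes of these analyses, a subgroup analysis may be performed". It would "compare the subjects with high change in expiratory muscle thickness, to a group with low change in expiratory muscle thickness", and of the dividing line it says: "A cutoff value to divide these groups will be determined based on how data will emerge". For function it states: "Variables as respiratory function measurements can be compared between groups with a Student's t-test, using group average values". For weaning, "a Kaplan-Meier survival analysis will be carried out to quantify differences in time to wean between groups".

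**The concern.** Once change is reduced to high or low, patients just either side of the cut count as opposites, and patients far apart on the same side count as equal. The result is a difference between two groups whose size depends on where the line falls. The function objective asks instead how function varies with thickness change.

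This cost is separate from the choice of cutoff. Fixing the cutoff in advance would remove the data-driven choice but not the loss of information. At stake is a stated secondary objective in a cohort of 100: its one named analysis is both optional and inefficient. For weaning, the only method that could deal with incomplete follow-up is the grouped one.

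**Working it through.** **1. Which analysis covers which outcome**

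- Respiratory function (MIP, MEP, cough peak flow): t-test between high and low groups, optional. No continuous analysis is named.
- Days to wean and ventilation duration: linear regression with nadir change continuous.
- Total ventilator time: linear regression with 5-day change continuous.
- Time to wean as a time-to-event outcome: Kaplan-Meier by high and low group only.

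**2. The plan's own figure.** The Sample size row gives 100 subjects, with no alpha, power, effect size or standard deviation. It cannot be reproduced, and the plan states no figure for information loss. The inputs below other than 100 are therefore assumptions.

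**3. Information kept by a split.** Assume a normal exposure, a linear effect and a fixed cut that puts a proportion p in one group. The efficiency relative to continuous use is φ(z_p)² / [p(1−p)].

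- 50/50: φ(0)² / 0.25 = 0.637, a loss of 36.3%. 100 patients count as about 64.
- 25/75: φ(0.6745)² / 0.1875 = 0.539, a loss of 46.1%. 100 patients count as about 54.
- Between these: 37.8% at 40/60, 40.5% at 33/67, 42.4% at 30/70.
- Beyond them: 51.0% at 20/80, 65.8% at 10/90.

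**4. Power at N = 100.** Assume two-sided alpha 0.05 and complete data. Power ≈ Φ[atanh(r)·√(N−3) − 1.960].

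- The correlation detected with 80% power on the continuous scale is r = tanh[(1.960 + 0.842)/√97] = 0.277.
- After a median split the effective correlation is 0.277 × √0.637 = 0.221, and power is 60%.
- After a 25/75 split it is 0.277 × √0.539 = 0.203, and power is 53%.
- Simulation (10,000 data sets per split, Pearson's test against the t-test): 80% continuous, 61% at the median, 54% at 25/75.

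**5. If function is available in fewer patients.** For an assumed N = 50 and r = 0.4, the same formula gives 83% continuous, 62% at the median and 54.5% at 25/75.

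**6. Other shapes of thickness change.** The loss is 1 minus the squared correlation between the exposure and its split indicator. At a median split it is 25% for a uniform distribution, 25% for a two-peaked normal mixture, 48% for a lognormal (log-SD 0.5), 50% for a t with 4 degrees of freedom and 52% for an exponential. With a quarter of patients on one side, the same shapes give 36% to 75%, depending on shape and on which tail is cut.

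**7. Kaplan-Meier.** Steps 3 to 6 concern a t-test on a continuous outcome, and no survival comparison was simulated. The same loss applies to time to wean only approximately, when the effect on the log hazard is small and linear and censoring depends little on the exposure.

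**The case against.** The strongest reply concerns weaning. A reader might infer that time to wean, like function, is analysed only through the split. The documents do not support that: the SAP already relates continuous change to days to wean and to total ventilator time. It makes nadir change the dependent variable in the first of these, but that costs no power, because in simple linear regression the slope test is the same in either direction. This part of the reply stands. What remains for weaning is narrower: those regressions handle neither censoring nor death before weaning, and the one time-to-event method uses the two groups.

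Second, the list of continuous variables is open-ended, so function could be regressed on change under it. That is possible but not planned. The measures are not named there, whereas the t-test between groups is written out for them.

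Third, the split is optional and labelled a subgroup analysis, so it is not a firm commitment. That is correct, but it leaves the function objective with no committed analysis at all.

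Fourth, a reader might infer that function is measured in only some patients. The Study parameters row ends its list of function measures with a restriction to selected patients, which may apply to the whole list or only to diaphragm pressure and electrical activity. The result at N = 100 does not depend on this.

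**Conclusion.** The point holds for respiratory function, and in a narrower form for weaning. The only named analysis of function and the only time-to-event analysis of weaning use a two-group version of a continuous exposure. For the t-test on function the loss is about 36% at a median split to 46% at 25/75, even with a cutoff fixed in advance. In power terms, 80% becomes about 60% or 53% at N = 100.

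These figures assume a roughly normal thickness change, a linear effect, splits between 50/50 and 25/75, two-sided alpha 0.05 and complete data. A reader might take 36% to 46% as a property of this plan. It is not, because the documents fix neither the cutoff nor the distribution. At a median split the shapes tried gave about 25% to 52%. For Kaplan-Meier the range is only a rough guide.

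The objectives affected are secondary and the primary comparison is untouched, but the loss is avoidable with data already planned. The SAP should be changed.

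**What to change.** **Function.** Make linear regression of MEP, MIP and cough peak flow on signed, continuous thickness change the main analysis of this objective. Report the effect per 10% change with a 95% confidence interval, and check the functional form, for example with a squared term. Name one change measure: the SAP uses nadir, 5-day and baseline-to-last change in different places, and the subgroup text does not say which defines high and low. Baseline to last measurement is one option.

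**Time to wean.** Use a time-to-event regression with change kept continuous. Nadir or last-measurement change should not enter as a fixed baseline predictor, because both are observed during the weaning follow-up and so depend on its length. Use the 5-day change the SAP already mentions and start follow-up at day 5, or enter change as a time-varying covariate. Treat death before weaning as a competing event. State whether day 5 counts from the start of ventilation or from the baseline scan, since inclusion is allowed up to 48 hours into ventilation.

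**Groups.** Keep the high and low groups and the Kaplan-Meier curves as illustration only.

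**Cost.** No new data are needed, but this is more than a one-line edit: the change measure, the time origin and the competing event must be specified, and the functional form checked. With a day-5 start, patients weaned or dead before then drop out of that analysis, and their number should be reported.
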